8.4 Statistical and analytical plans

The data will be summarized using the software package SAS release 9.1 or higher (SAS Institute Inc., Cary, North Carolina [NC], United States of America [USA]). All data will be listed and summary tables will be provided. The number of data available and missing data, mean, standard deviation, and other summary statistics will be calculated for continuous data. Frequency tables will be generated for categorical data. No formal statistical tests will be performed.

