The main evaluation period of the study has a duration of 6 months. The 6-month data for PTPs will be analyzed for regulatory purposes as a final analysis of the main study in PTPs, nevertheless, Part B and the extension for both parts will be ongoing. When safety has been assessed in 10-20 PTPs who have received at least 50 EDs, enrollment will begin in Part B. All subjects will have the option of continuing in the extension trial. The overall study will be closed after all subjects in Parts A and B have completed their respective extensions. Additional analyses will summarize data from Part B and the extension trials.

2. Study Objectives

Primary objective

• To demonstrate the safety and efficacy of treatment with BAY 81-8973 for prophylaxis and breakthrough bleeds in children with severe hemophilia A

Secondary objectives

- To assess the safety and efficacy of BAY 81-8973 during surgeries
- To assess incremental recovery of BAY 81-8973
- To characterize pharmacokinetics in a subset of a minimum of 6 previously treated patients (PTPs) or previously untreated patients (PUPs)

3. Study Design

From the protocol:

This is a phase-III multicenter, open-label uncontrolled study to demonstrate safety and efficacy of treatment with BAY 81-8973 for prophylaxis, breakthrough bleeds, and surgeries in children with severe hemophilia A. The study will be conducted worldwide.

The study is divided into two parts: Part A will investigate a total of 50 PTPs up to 12 years of age. Part B will include 25 PUPs. All subjects will receive prophylactic administration of BAY 81-8973. Subjects in Part A will be treated with 25-50 IU/kg at least 2x a week, or more frequently as needed for prophylaxis. Treatment in Part B may begin with start of prophylaxis with 15-50 IU/kg (minimum dose 250 IU) at least one day a week, or with the subject's first bleeding event. The study drug will be used both for treatment of bleeding events and prevention of bleeds with surgical procedures. Individual subject dose decisions are at the discretion of the investigator.

Enrollment will be staggered. Part A will start after 20 adult/adolescent subjects have received 50 EDs with BAY 81-8973 without safety concerns in previous studies with BAY 81-8973. PTPs age 6 to 12 years will begin enrollment first, followed by PTPs <6 years. Part B, for PUPs, will begin enrollment after 20 children in Part A have had 50 ED.

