3.1 Sample size calculation

Sample size has been determined according to the requirements set forth by guideline CPMP/BPWG/1561/99 (Note for Guidance on the Clinical Investigation of Recombinant Factor VIII and Factor IX Products), and taking into account the revised draft version, CHMP/BPWP/144533/09. Age groups are in accordance with the International Conference on Harmonization (ICH)/CPMP guideline E11 (Clinical Investigation of Medicinal Products in the

Pediatric Population) and sample sizes have been confirmed on consultation with the European Medicines Agency Pediatric Committee [EMA/PDCO] on submission of the Pediatric Investigation Plan.

Adolescents and adults are included in 2 ongoing efficacy and safety studies of the clinical development program of BAY-81-8973. This pediatric study consists of two parts. Part A will include a total of 50 PTPs; 25 subjects >6 - 12 years and 25 subjects aged 0-6 years. Part B will enroll at least 25 up to a maximum of approximately 50 PUPs aged 6 years and under. Total sample size will be at least 75 subjects up to a maximum of approximately 100 subjects.

4. General Statistical Considerations

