5.1 Assignment of analysis sets

The safety analysis set (SAF) will include all subjects who were entered into the study and received study drug. The intent-to-treat analysis set (ITT) will include all subjects in the SAF who have infusion/bleeding data from the EPD. The per-protocol analysis set (PPS) will include all ITT subjects who have no major protocol deviations and have EPD data. The ITT will be used for the primary efficacy analysis. The efficacy analysis of the PPS will be considered supportive. Data from Part B and the extensions will be summarized separately.

Specific rules for major protocol deviations will be documented in the "Protocol Deviations Document" (PDD) prior to validity review meeting. Final decisions regarding the assignment of subjects to analysis sets will be made during the Validity Review Meeting and documented in the Validity Review Report.

Subjects will be excluded from the PPS for non-compliance if they violate any of the following criteria (for PTPs only):

- at least 1 interval between all infusions > 30 days
- at least 2 intervals between all infusions > 21 days
- at least 3 intervals between all infusions > 14 days
- number of infusions < 80% number of expected infusions [use expected number of infusions = (prescribed number of infusions per week) * (last datetime in study 1st datetime in study) / (60*24*7)]
- at least 20% of prophylaxis infusions at a dose level < 15 IU/kg (for PTPs)
- at least 20% of prophylaxis infusions at a dose level < 10 IU/kg (for PUPs) [Note: not applicable to this SAP)

All tables will summarize data with columns for PTP 0-<6 years, PTP 6-12 years, and Total.

Pharmacokinetic Analysis Set

All subjects with evaluable PK-data will be included in the analysis of pharmacokinetic data.

Subgroups:

Subgroup tables will be provided. Possible subgroups for number of bleeds within 48 hours after prophylaxis per year and number of bleeds per year to be presented are:

- Prophylaxis Treatment regimen (<=2x/week, >2x/week)
- Average prophylaxis dose high (>=30 IU/kg), low dose (<30 IU/kg)
- Average prophylaxis dose/week high (>=80 IU/kg), low (<80 IU/kg)
- prior treatment (on-demand, prophylaxis)
- Race Group (white, non-white)
- Region (North America, Europe, Israel)
- Number of Bleeds during previous 12 months (<median, >=median)
- Number of Joint Bleeds during previous 12 months (<median, >=median)
- Presence of Target Joint (no, yes)

6. Statistical Methodology

6.1 **Population characteristics**

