6.4 Safety

All subjects receiving any amount of study drug will be included in the safety analysis. Laboratory findings, adverse events, concomitant medications, and medical history data will be provided in subject listings.

Laboratory values, incidence of high or low abnormal values, changes from baseline (Baseline value is the last value before the first study drug infusion.) will be summarized. Vital signs will be summarized. Individual listings of AEs [including AEs as reported, start, duration, severity, relation to study drug] will be provided. The incidence of treatment-emergent AEs will be summarized using the Medical Dictionary for Regulatory Affairs (MedDRA). AEs with a start date prior to first infusion or more than 3 days after the last infusion are not treatment emergent. Treatment emergent determination will be derived after missing or incomplete AE start date is imputed. Imputation rules for missing and incomplete AE start are described in Section 4.3

Two laboratory analytes, Anti HSP70 and Anti BHK, will be summarized in a listing that will include all values for those subjects with any positive result. Incidence of HSP-70 antibody formation and hamster protein antibody formation will be assessed from these laboratory tests.

Inhibitor development, as measured by Bethesda assay, as well as the results from all ELISA assays, will be summarized by preparation and timepoint and presented in subject listings. The frequency of subjects who develop positive inhibitor titers (Bethesda ≥ 0.6 BU) will be presented.

Vital signs and change from baseline of vital signs will be summarized with descriptive statistics distinguishing pre-infusion and post-infusion readings. Baseline is the last measurement before the first study drug infusion. Post-infusion minus pre-infusion values will be summarized at Month 1, Month 2, and final visit in the main study.

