The study is divided into two parts: Part A will investigate a total of 50 PTPs up to 12 years of age. Part B will include at least 25 PUPs, plus up to additional 25 PUPs/MTPs (as of Amd 6). All subjects will receive prophylactic administration of BAY 81-8973. Subjects in Part A will be treated with 25-50 IU/kg at least 2 times per week, or more frequently as needed for prophylaxis.

Treatment in Part B may begin with start of prophylaxis with 15-50 IU/kg (minimum dose 250 IU) at least one day a week, or with the subject's first bleeding event. The study drug will be used both for treatment of bleeding events and prevention of bleeds and with surgical procedures. Individual subject dose decisions are at the discretion of the investigator (as of Amds 1 and 3).

Statistical Analysis Plan PH-41074

Protocol No.: BAY 81-8973 / 13400

Page: 6 of 19:

Enrollment will be staggered. Part A will start after 20 adult/adolescent subjects have received 50 ED with BAY 81-8973 without safety concerns in previous studies with BAY 81-8973. PTPs age 6 to 12 years will begin enrollment first, followed by PTPs <6 years (as of Amd 3). Part B, for PUPs/MTPs (as of Amd 6) will begin enrollment after 20 children in Part A have had 50 ED. As of Amd 7, enrollment in Part B will be staggered. 10 patients will be enrolled, and will commence treatment for 20 ED. While safety assessment of the first cohort is ongoing, screening for the next sequence of 10 patients will continue. Treatment of next sequence/10 patients will start if no safety concerns are identified in the previous cohort following completion of 20 EDs. In the event patients would require FVIII treatment, they could still be eligible according to protocol definitions in case no more than 3 EDs of an alternative FVIII product has been administered.

Enrollment will be suspended if the inhibitor rate in the first cohort exceeds 50% following discussion with an independent Data Monitoring Committee (DMC) (as of Amd 7). The total study duration (including screening period) per subject in Part A (as of Amd 1) will be approximately 6-8 months (as of Amd 1) during which the subjects will accumulate at least 50 ED. For Part B, subjects will continue in the study until achieving 50 ED.

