6.4.3 Laboratory parameter

Laboratory values, incidence of high or low abnormal values, and changes from baseline will be summarized. In general only central laboratory values will be used for analysis. Where also local values are taken into consideration will be explicitly mentioned.

Two laboratory analytes, Anti HSP-70 and inhibitors, will be summarized in a listing that will include all values for those subjects with any positive result. Incidence of HSP-70 antibody formation and inhibitors will be assessed.

Inhibitor development, as measured by Bethesda assay will be summarized timepoint and presented in subject listings. The frequency of subjects who develop positive inhibitor titers (Bethesda ≥ 0.6 BU) as well as high titer (> 5.0 BU) will be presented. For the inhibitors as well as for the high titer inhibitors Kaplan Meier graphics for the occurrence will be provided.

A positive inhibitor testing is defined with a threshold of ≥ 0.6 BU in the central laboratory and a confirmation by

- a second plasma sample and a positive central testing or
- two consecutive local measurements (2^{nd} and 3^{rd} sample) with doubled threshold (Bethesda ≥ 1.2 BU).

In case a central value of the same samples used for local confirmation shows no inhibitor, the local confirmation is not valid.

High titer inhibitor needs not to be confirmed by a second high (> 5.0 BU) value, but the inhibitor itself needs a confirmation.

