2.1 Secondary Endpoints

The secondary parameters are the following:

- Annualized number of total bleeds (sum of spontaneous bleeds, trauma bleeds, untreated bleeds, and 'other' bleeds) during prophylaxis treatment
- Hemostatic outcome of surgeries (both major and minor) including blood loss, transfusion, and/or hemostatic-related surgical complications
- Inhibitor development, as measured by Nijmegen modified Bethesda assay
- FVIII recovery values
- Pharmacokinetics (in a subset of children)

The annualized number of total bleeds will be calculated as described in section 4.5.2 of the SAP 2.0 and summarized accordingly.

The hemostatic outcome of surgeries will presented in a subject listings.

The incidence of inhibitor development during the total part B period will be presented in a summary table, additionally a subject listing will be provided relating the number of total exposure days to the corresponding FVIII Inhibitor value.

The FVIII recovery values will be calculated as described in section 4.7 of the SAP 2.0 and summarized accordingly. In addition, a subject listing will be provided.

The summary of pharmacokinetic values in Part B of the study will only be presented in the final report for the extension study due to the limited number of collected samples.

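### No confidence interval is planned for the inhibitor rate in either SAP or either supplement, although the protocol promises a rate and the group sizes (25 to 50) leave it imprecise

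*SAP*

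**What the plan says.** Both SAPs (section 2 of each) and the protocol synopsis give the primary objective as "To demonstrate the safety and efficacy of treatment with BAY 81-8973 for prophylaxis and breakthrough bleeds in children with severe hemophilia A". Protocol section 2 uses the milder verb evaluate. Protocol 8.3 undertakes to determine the rate of inhibitor development and counts inhibitor-free children in the denominator only if they have at least 50 exposure days (ED). Protocol 7.5.1.1 makes every inhibitor a serious adverse event.

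The planned inhibitor outputs are:

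- **Part A SAP v2.1, 6.4:** summaries by preparation and timepoint, subject listings, and "The frequency of subjects who develop positive inhibitor titers (Bethesda ≥ 0.6 BU) will be presented". Section 5.1 sets the layout: "All tables will summarize data with columns for PTP 0-<6 years, PTP 6-12 years, and Total".
- **Part B SAP v2.0, 6.4.3:** the frequency of confirmed inhibitors "as well as high titer (> 5.0 BU) will be presented. For the inhibitors as well as for the high titer inhibitors Kaplan Meier graphics", with timepoint summaries and listings. Section 4.1 limits frequency tables to number and percentage, and gives safety data for PUPs, minimally treated patients (MTPs) and total.
- **Part B SAP Supplement 1.0, 2.1:** "The incidence of inhibitor development during the total part B period will be presented in a summary table", plus a listing of inhibitor values against exposure days. Inhibitor development is listed there as a secondary parameter.

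The Part A supplement of July 2013 does not touch inhibitors. Protocol 8.4 says "No formal statistical tests will be performed". Sample sizes follow regulatory guidelines (protocol 8.6; Part A SAP 3.1), and the Part B SAP appendix 9.1 states that no formal determination was made. No confidence interval, upper bound or acceptable inhibitor rate appears in any of these sections.

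**The concern.** A percentage from 25 to 50 children says little about the underlying rate unless its uncertainty is shown beside it. Here precision was addressed neither when the sample size was set nor in the planned tables. If the plan is followed as written, the report will show entries such as 0/50 (0%) or 8/25 (32%) and stop there.

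The two parts are exposed differently. In PTPs the risk is that no events in a small group is read as a low rate. In PUPs and MTPs events are expected, because the Part B SAP introduction puts the incidence in severe disease at up to half of patients. There the risk is that a percentage looks better than that background figure when the data cannot separate the two. In both parts, a statement that safety has been demonstrated would go out without the quantity needed to judge it.

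**Working it through.** **Inputs**

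- Part A size (Part A SAP 3.1): "Part A will include a total of 50 PTPs; 25 subjects >6 - 12 years and 25 subjects aged 0-6 years". The age boundary is worded differently in 5.1, but each column is still about 25, and 25 + 25 = 50.
- Part B size (Part B SAP section 3; protocol 8.6): at least 25 PUPs plus about 25 further PUPs/MTPs, so 25 to about 50.
- The documents give no planned power, precision or acceptable rate for inhibitors, so there is no figure of theirs to reproduce.
- Assumptions: the true PTP rates (1% to 5%) and the Part B counts below are illustrative.

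**Interval.** For x events in n, the Clopper-Pearson two-sided 95% limits are the 2.5% quantile of Beta(x, n-x+1) and the 97.5% quantile of Beta(x+1, n-x). For x = 0 the upper limit reduces to 1 - 0.025^(1/n).

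**Part A, zero events**

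- n = 50: 1 - 0.025^(1/50) = 7.1%
- n = 25 (one age column): 1 - 0.025^(1/25) = 13.7%
- n = 42 (if, say, 8 inhibitor-free children fall short of 50 ED and leave the denominator): 1 - 0.025^(1/42) = 8.4%

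**Chance of seeing no inhibitors, (1-p)^n**

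| assumed true rate p | n = 25 | n = 50 |
|---|---|---|
| 1% | 78% | 60% |
| 2% | 60% | 36% |
| 3% | 47% | 22% |
| 5% | 28% | 8% |

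**Part B, exact 95% intervals**

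| result | estimate | interval | width in points |
|---|---|---|---|
| 8/25 | 32% | 14.9-53.5% | 38.6 |
| 16/50 | 32% | 19.5-46.7% | 27.2 |
| 10/25 | 40% | 21.1-61.3% | 40.2 |
| 20/50 | 40% | 26.4-54.8% | 28.4 |

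The first two rows show the practical point. The same 32% is compatible with a true rate of one half in 25 children and not in 50, and a table of number and percentage does not display that. In the other direction, if the true rate were 50%, 25 PUPs would still show 40% or less (10 or fewer) with binomial probability 0.21.

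**Is a near-empty result realistic in Part B?** At true rates of 30% and 50%, the chance of 3 or fewer inhibitors in 25 is 3.3% and 0.008%. So the zero-event argument belongs to Part A only; in Part B the issue is the width of the interval.

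**The case against.** The strongest case against has five parts.

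1. *The plan is openly descriptive, and the sizes were set by guideline and confirmed with the EMA paediatric committee.* True. But an interval is estimation, not a test, and protocol 8.3 promises a rate.

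2. *Anyone can compute the interval from n and the percentage.* True for a raw proportion whose denominator is clear. Here it is not: neither SAP repeats the 50-ED rule. Nor can limits be recovered from a Kaplan-Meier graphic for which neither limits nor numbers at risk are specified.

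3. *The Part A analysis is finished.* The Part B SAP introduction confirms that it has been reported, so nothing can now be pre-specified there. This stands, and it moves the fix to Part B and the final overall analysis.

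4. *Both SAPs leave table details to separate TLF specifications.* These are not among the documents reviewed and could contain intervals. The gap is therefore established for the protocol, the SAPs and the supplements only.

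5. *Safety is also protected by SAE reporting, independent data monitoring and staggered enrollment.* True, but these govern conduct, not how precisely the final rate is reported.

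A reader might also infer that both SAPs report nothing beyond a bare frequency. The Part B outputs (high-titer frequency, Kaplan-Meier graphics, incidence table, exposure-day listing) contradict that. Nor do the documents name inhibitors as the main safety outcome: they are called the most significant treatment complication, and the Part B supplement lists them as a secondary parameter.

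**Conclusion.** The point holds as a gap in planned reporting. The protocol, SAPs and supplements promise an inhibitor rate under an objective of demonstrating safety and plan no measure of its precision. The size is material: upper limits of 7.1% to 13.7% after no events in PTPs, and intervals roughly 27 to 40 points wide at the Part B results illustrated.

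Three stronger readings are not supported:

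- **That the groups are too small to exclude a relevant rate.** No acceptable rate is stated, so this cannot be decided from the documents. 0/50 excludes rates above 7.1% but not rates of 1% to 5%.
- **That zero inhibitors in 50 PTPs is the likely result at a true 2% to 3%.** At 36% and 22% it is plausible; at least one event is more probable.
- **That one half is the margin Part B must beat.** The SAP's figure is background and the top of a range. The only operational 50% is the suspension rule for the first staggered Part B cohort, applied after discussion with the monitoring committee (protocol section 4).

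The figures assume the planned numbers are reached; fewer evaluable children would widen every interval.

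**What to change.** In Part B SAP 6.4.3, Supplement 1.0 section 2.1 and the plan for the final overall analysis (protocol 8.5), add:

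- The inhibitor proportion will be given with an exact (Clopper-Pearson) two-sided 95% confidence interval: any inhibitor and high-titer inhibitor for PUPs, MTPs and total; any inhibitor for PTPs, in total and by age group. PTPs enter through the final overall analysis because their main report is complete.
- The denominator will follow protocol 8.3 (inhibitor-free subjects need at least 50 ED), with n stated in each cell.
- Kaplan-Meier estimates for any and high-titer inhibitor will be tabulated on the exposure-day scale, with pointwise 95% limits at 20 and 50 ED. Section 6.4.3 does not state the time scale of the graphics, so it should be named.
- The conclusion on inhibitor safety will be worded in terms of the interval, not the percentage alone.

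No hypothesis test is introduced, so protocol 8.4 is unaffected. The cost is a few sentences of SAP text, one more column in existing tables and a short Kaplan-Meier table, with no new data or patients. The one downside is that the stated result looks less favourable, for example 0% with an upper limit of 7.1%. If the TLF specifications already contain these intervals, a reference to them in the SAP is enough.

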6.5 Additional analyses planned to be reported outside the main report

Data from Part B and the extensions will be summarized separatly.

7. Document history and changes in the planned statistical analysis

Version 1.1 03 May 2012 This is the first version of the SAP to be signed off. Previous versions including V1.0 were circulated internally.

Version 2.1 19 Dec 2012 Many minor changes to be consistent with the TLF developed from 3 recent meetings and protocol version 3.0, added ADMAP macro reference, and changed dataset names.

8. References

n/a

A multi-center Phase III uncontrolled open-label trial to evaluate safety and efficacy of BAY 81-8973 in children with severe hemophilia A under prophylaxis therapy

BSP study drug	BAY 81-8973		
Study purpose:	To demonstrate the safety and efficacy of treatment with BAY 81-8973 for prophylaxis and breakthrough bleeds in children with severe hemophilia A		
Clinical study phase:	Phase III	Date:	18Jul2013
Study No.:	13400	Version:	1.0

• Section 4.4, revised text:

The 6 month data for PTPs will be analyzed for regulatory purposes as a final analysis of the main study. This analysis is considered an interim analysis in the protocol because the trial is ongoing in the extension phase and an overall analysis of the whole study is planned after study completion.

• In Sections 4.1 and 6.2, the definition of total bleeds should read as follows:

The primary variable is the annualized number of total bleeds (sum of spontaneous bleeds, trauma bleeds, untreated bleeds, and infusions with reason = other) that occur within 48 hours after all prophylaxis infusions.

• Section 6.2:

All efficacy variables will be summarized using the ITT analysis set. The primary efficacy variable and the FVIII recovery results will also be summarized using the PPS, which will be supportive for the primary efficacy analysis, but will be considered the primary analysis for the FVIII recovery.

Title page

A multi-center Phase III uncontrolled open-label trial to evaluate safety and efficacy of BAY 81-8973 in children with severe hemophilia A under prophylaxis therapy

Leo Kids PUPs (Part B and extension) Interim Analysis

Bayer study drug	BAY 81-8973		
Clinical study phase:	III	Date:	22 Jan 2020
Study No.:	13400	Version:	2.0
Author:	PPD דיט		

Confidential

